**Logistic regression model:**

Certain binary outcome variables, e.g. response outcomes, will be evaluated using a logistic regression model with treatment regimen, weight, stratum if applicable. Odds ratios will be computed for comparisons of AIN457 regimens versus control(s) utilizing the logistic regression model fitted.

**SAS code for logistic regression:**

```
Proc logistic data=aaa;  
Class TRT STRATA / param=glm;  
Model AVAL = TRT WEIGHT STRATA;  
Lsmeans TRT / diff cl exp;  
Ods output diffs=lsml_diff;  
Run;
```

In cases where separation is a concern for the primary endpoint at Week 12, e.g. 0% or 100% response in one treatment (sub)group, an exact logistic regression model will be applied to all visits. To ensure convergence, this model will not include any continuous covariates.

```
Proc logistic data=aaa exactonly;
Class TRT STRATA / param=glm;
Model AVAL = TRT STRATA;
Exact TRT / estimate=both;
Ods output exactoddsratio=exactoddsratio;
Run;
```

When exact logistic regression is unable to be implemented (due to computational complexity as the procedure can lead to extremely long run times), then Fisher's exact test will be applied for each AIN457 group versus placebo comparison. In this case, no odds ratios or confidence intervals can be estimated due to 0% response in one of the groups, but p-values may be calculated.

```
Proc freq data=aaa;
Table TRT * AVAL / fisher;
Where TRT in ( "AIN457 xx mg" "Placebo" );
Run;
```

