### 2.5.1 Estimand of primary variable

Proportion of patients fulfilling ASAS20 criteria in the pooled Secukinumab groups and Placebo regimen at Week 12. The analysis of the primary endpoint will be based on the FAS population. The analysis of the primary variable will be based on the following estimand:

- Population: patients in full analysis set
- Variable of interest: proportion of patients achieving treatment response as defined by the ASAS20 criteria at Week 12.
- Intervention effect: effect between a secukinumab pooled groups vs. placebo regardless of adherence to randomized treatment.
- Summary measure: Odds ratio (OR) of ASAS20 response for secukinumab pooled groups and placebo

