### 2.5.2 Statistical hypothesis, model, and method of analysis of primary estimand

The statistical hypothesis for ASAS20 being tested is

$$H_0 : p_1 = p_0$$

v/s

$$H_1 : p_1 \neq p_0$$

where  $p_0$  denotes the proportion of ASAS20 responders in the placebo and  $p_1$  denotes the proportion of ASAS20 responders in the pooled Secukinumab groups at week 12.

Secukinumab groups will be pooled using their measurements at week 12.

The primary analysis will be performed using logistic regression with treatment, TNF- $\alpha$  status (previously exposed / never exposed), and CRP status (above central lab ULN / equal or below central lab ULN) as factors. The two Secukinumab groups will be pooled using a linear contrast.

Odds ratios and 95% CI will be presented comparing the Secukinumab (pooled) groups to placebo.

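### SAP 5.4 prints no program for the primary (H1) analysis of 2.5.2, and its separation fallback, triggered by the primary endpoint, contains no pooled secukinumab versus placebo test

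*SAP*

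**What the plan says.** **Primary analysis.** SAP 2.5.2 lists treatment, TNF status (previously or never exposed) and "CRP status (above central lab ULN / equal or below central lab ULN) as factors". It adds: "The two Secukinumab groups will be pooled using a linear contrast". Protocol 9.4.2 specifies the same model and contrast. The summary measure in SAP 2.5.1 is a single "Odds ratio (OR) of ASAS20 response for secukinumab pooled groups and placebo".

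**SAP 5.4.** The text before the program says that certain binary outcomes "will be evaluated using a logistic regression model with treatment regimen, weight, stratum if applicable". The standard program has the model line "Model AVAL = TRT WEIGHT STRATA" and the comparison line "Lsmeans TRT / diff cl exp".

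**Fallback.** The next paragraph begins "In cases where separation is a concern for the primary endpoint at Week 12" and gives as examples 0% or 100% response in a treatment group or subgroup. It then moves all visits to exact logistic regression on treatment and stratum, without continuous covariates. If that cannot be run, "Fisher's exact test will be applied for each AIN457 group versus placebo comparison".

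**Gate.** Under SAP 2.7.2, H1 is tested first. The level passes to H2 and onward only if H1 is rejected and the effect favours secukinumab. SAP section 4 records no change from the protocol.

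**The concern.** The 5.4 code is what a programmer would start from, and it differs from 2.5.2 in covariates, contrast and response level. For the standard program this is a missing primary version: 2.5.2 still says what to do. The fallback is different. It is a stated rule, it names the primary endpoint, and it replaces the pooled comparison with tests that do not address H1. If it were used, the sponsor would have to decide after seeing the data how to test the hypothesis that opens the whole confirmatory family. Pooling was introduced by the amendment to keep power, and a per-arm test gives that up.

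**Working it through.** **1. Side by side**

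| Element | SAP 2.5.2 / protocol 9.4.2 | 5.4 standard program | 5.4 exact model | 5.4 Fisher step |
|---|---|---|---|---|
| TNF status | yes | probably, through STRATA (the randomisation stratum) | probably, through STRATA | no |
| CRP status | yes | no | no, although categorical | no |
| Weight | no | yes | no | no |
| Pooled contrast | yes | no, pairwise differences only | no, treatment factor only | no, each arm separately |
| Response level | ASAS20 response | not set | not set | not applicable |

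With a three-level treatment factor, the standard program gives three pairwise odds ratios and no row for H1. The exact model tests the treatment factor and estimates its parameters. The Fisher step tests comparisons of the H4 and H5 kind.

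**2. The plan's own figures (context only)**

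Inputs from SAP section 3: 56.9% versus 27.0%, 90% power, two-sided 5%.
- Mean rate = (0.569 + 0.270)/2 = 0.4195.
- n = [1.96 × √(2 × 0.4195 × 0.5805) + 1.2816 × √(0.569 × 0.431 + 0.27 × 0.73)]² / 0.299² = 55.1, so 56 per group.
- With continuity correction: (55.1/4) × [1 + √(1 + 4/(55.1 × 0.299))]² = 61.6, so 62. This matches the plan.
- The stated 78% power for the pooled comparison at 35% placebo response is approximately recovered. Exact enumeration of the continuity-corrected test at 127 versus 63 gives 76.9%. The uncorrected normal approximation gives 82.0% at 190 patients and 78.3% at 190 × 62/68 = 173.

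**3. How likely is the fallback?**

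Whole arm, 190/3 ≈ 63 patients: P(no placebo responders at 27%) = 0.73^63 ≈ 2 × 10⁻⁹. It is smaller still at 35%. All responders in an active arm at 56.9% is rarer again.

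Subgroup of an arm, size m, placebo rate 27%: P(no responders) = 0.73^m. The plan gives no cell sizes, so m is an assumption:
- m = 25 (the 40% TNF cap: 76/3): 0.0004
- m = 10 (30% TNF-exposed, half of them with high CRP: 190 × 0.3 × 0.5/3 = 9.5): 0.043
- m = 5: 0.21

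One empty cell of this kind does not by itself stop the main-effects model of 2.5.2 from fitting. The wording of the rule would still allow the switch.

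**4. What the per-arm test loses**

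Exact power of Fisher's test at 35% versus 56.9%: one arm versus placebo (63 versus 63) 66.5%; pooled versus placebo (127 versus 63) 80.6%.

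**5. Response level**

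PROC LOGISTIC models the lowest ordered level unless told otherwise. If AVAL is 1 for responders and 0 for non-responders (coding not given):
- 56.9% versus 27.0%: (0.569/0.431)/(0.27/0.73) = 3.57; prints as 1/3.57 = 0.28.
- 56.9% versus 35%: (0.569/0.431)/(0.35/0.65) = 2.45; prints as 0.41.

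**6. Illustration on one simulated data set of 190**

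Assumed: 30% TNF-exposed, 50% high CRP, weight SD 15 kg, and log-odds effects of −0.6, +0.8 and −0.015 per kg. The 2.5.2 model with its contrast gives a pooled odds ratio of 2.23 (95% CI 1.17 to 4.24). The 5.4 model prints 2.53 (delayed versus placebo), 1.82 (early versus placebo) and 1.39 (delayed versus early). A contrast added to it would give 2.15 (1.14 to 4.07). The two models give similar answers here but not the same one.

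**The case against.** The best defence is that 5.4 is a code appendix and not a second specification. Its text is limited to certain binary outcomes, its weight term fits the secondary ASAS20 models in 2.7.2, and placeholder dataset and dose labels show that it was not meant to run as printed. That defence stands for the standard program. A reader might infer that the SAP contains two competing primary models. The documents do not support this: 2.5.2 and the protocol are identical, section 4 declares no change, and nothing labels the 5.4 model line as primary.

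A reader might also infer that the primary odds ratio cannot be obtained. That goes too far, because 2.5.2 defines it in words. It could even be rebuilt by hand from pairwise output, though with the wrong covariates. Recoding treatment to two levels would print a pooled odds ratio, but not from the contrast model.

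A further inference is that the odds ratios will print inverted. That depends on coding the plan does not state, and an odds ratio below 1 beside a higher secukinumab response rate would be noticed.

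It can also be said that separation will never occur. That is right for a whole arm. It is not secure for subgroups, which the rule includes and does not define.

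The template defence does not cover the fallback, because that paragraph names the primary endpoint.

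**Conclusion.** The point holds as an implementation gap and a wrong fallback rule. The primary analysis itself is defined. SAP 5.4 has no program that matches it, and if the fallback is used, neither of its two steps tests pooled secukinumab against placebo, so the gatekeeping hypothesis would lack its planned test. The chance of this is negligible through a whole arm. It is not negligible if small subgroup cells count: 0.04% to 21% per placebo cell for assumed sizes of 25 down to 5 at 27% response. The odds-ratio inversion is a secondary matter, conditional on 1/0 coding, and leaves two-sided p-values unchanged. The direction condition in the testing strategy is still a reason to state the response level. The simulated odds ratios are illustrative only.

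**What to change.** In SAP 5.4, before database lock:

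1. State that 2.5.2 governs H1 and that the existing program is for other binary endpoints.
2. Print the primary program: `model AVAL(event='1') = TRT TNF CRP`, all three as class factors, with an ESTIMATE of 0.5, 0.5, −1 for delayed, early and placebo in that order, exponentiated with a 95% CI. Define AVAL as 1 for a responder.
3. For H1, make the fallback an exact test of pooled secukinumab versus placebo. Keep TNF and CRP status in the exact logistic model, and use a pooled-versus-placebo Fisher test if that model cannot be run. Say what counts as separation, and whether an empty subgroup cell qualifies when the 2.5.2 model still fits.
4. Add the event level to the secondary code.

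The cost is a few lines of SAP text and code. No data collection, sample size or hypothesis changes.

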## 5.5 Score derivations and response criteria

### 5.5.1 Assessment of Spondyloarthritis International Society (ASAS)

The ASAS response measures consist of the following assessment domains ([Sieper et al 2009](#)):

1. Patient's global assessment of disease activity measured on a VAS scale.
2. Patient's assessment of IBP, represented by either total or nocturnal pain scores, both measured on a VAS scale. For ASAS response analysis, the total back pain score will be used.
3. Function represented by BASFI average of 10 questions regarding ability to perform specific tasks as measured by VAS scale.
4. Morning stiffness, represented by the average of the last 2 questions on the 6-question BASDAI regarding morning stiffness as measured by VAS scale.

Additional assessment domains:

5. Spinal mobility represented by the BASMI lateral spinal flexion assessment
6. C-reactive protein (acute phase reactant)

#### ASAS response criteria (ASAS 20)

The ASAS Response Criteria (ASAS 20) was defined as an improvement of  $\geq 20\%$  and  $\geq 1$  unit on a scale of 10 in at least 3 of the 4 main domains and no worsening of  $\geq 20\%$  and  $\geq 1$  unit on a scale of 10 in the remaining domain. Or

The ASAS Response Criteria (ASAS 20) was defined as an improvement of  $\geq 20\%$  and  $\geq 10$  unit on a scale of 100 in at least 3 of the 4 main domains and no worsening of  $\geq 20\%$  and  $\geq 10$  unit on a scale of 100 in the remaining domain.

#### **ASAS response criteria (ASAS 40)**

The ASAS 40 response was defined as an improvement of  $\geq 40\%$  and  $\geq 2$  units on a scale of 10 in at least 3 of the 4 main domains and no worsening at all in the remaining domain.

#### **ASAS 5/6 improvement criteria**

The ASAS 5/6 improvement criteria is an improvement of  $\geq 20\%$  in at least five of all six domains.

#### **ASAS partial remission criteria**

The ASAS partial remission criteria are defined as a value not above 2 units in each of the four main domains on a scale of 10.

### **5.5.2 Ankylosing spondylitis disease activity score (ASDAS)**

The ASDAS (Sieper et al 2009, Lukas et al 2009) is a composite index to assess disease activity in AS. The ASDAS-C-reactive protein (CRP) will be utilized to assess the disease activity status.

Parameters used for the ASDAS include:

- Total back pain (BASDAI question 2)
- Patient global assessment of disease activity
- Peripheral pain/swelling (BASDAI question 3)
- Duration of morning stiffness (BASDAI question 6)
- CRP in mg/liter

Disease activity states: inactive disease, low disease activity, high disease activity, and very high disease activity. The 3 values selected to separate these states were  $< 1.3$  between inactive disease and low disease activity,  $< 2.1$  between moderate disease activity and high disease activity, and  $> 3.5$  between high disease activity and very high disease activity. Selected cutoffs for improvement scores were a change  $\geq 1.1$  unit for “minimal clinically important improvement” and a change  $\geq 2.0$  units for “major improvement” (Machado et al 2011).

The following formula will be used to derive ASDAS-CRP:

$$\text{ASDAS-CRP} = 0.121 \times \text{total back pain} + 0.110 \times \text{patient global} + 0.073 \times \text{peripheral pain/swelling} + 0.058 \times \text{duration of morning stiffness} + 0.579 \times \text{Ln}(\text{CRP}+1).$$
$$\text{ASDAS-ESR} = 0.08 \times \text{Back Pain} + 0.07 \times \text{Duration of Morning Stiffness} + 0.11 \times \text{Patient Global} + 0.09 \times \text{Peripheral Pain/Swelling} + 0.29 \times \sqrt{(\text{ESR})}$$

All assessments will be performed in 0-10 scale.

### **5.5.3 Bath ankylosing spondylitis disease activity index (BASDAI)**

The BASDAI consists of a 0 through 10 scale (0 being no problem and 10 being the worst problem, captured as a continuous VAS), which is used to answer 6 questions pertaining to the 5 major symptoms of axSpA:

1. Fatigue
2. Spinal pain
3. Joint pain/swelling
4. Areas of localized tenderness (called enthesitis, or inflammation of tendons and ligaments)
5. Morning stiffness duration
6. Morning stiffness severity

To give each symptom equal weighting, the mean (average) of the 2 scores relating to morning stiffness is taken (questions 5 and 6). The resulting 0 to 10 score is added to the scores from questions 1-4. The resulting 0 to 50 score is divided by 5 to give a final 0-10 BASDAI score. Scores of 4 or greater suggest suboptimal control of disease, and patients with scores of 4 or greater are usually good candidates for either a change in their medical therapy or for enrollment in clinical trials evaluating new drug therapies directed at AS. BASDAI is a quick and simple index taking between 30 seconds and 2 minutes to complete.

At least 4 questions should be non-missing to calculate the BASDAI score. Otherwise, BASDAI score will be missing (Haywood 2002). If both Q5 and Q6 are missing or one of Q1 to Q4 is missing the total sum should be divided by 4 instead of 5. If two of Q1 to Q4 is missing the sum should be divided by 3. BASDAI 50 response is defined as at least a 50% improvement (decrease) in total BASDAI score, as compared to the Baseline total BASDAI score.

### **5.5.4 Bath ankylosing spondylitis functional index (BASFI)**

The BASFI is a set of 10 questions designed to determine the degree of functional limitation in those subjects with AS. The ten questions were chosen with a major input from subjects with AS. The first 8 questions consider activities related to functional anatomy. The final 2 questions assess the subjects' ability to cope with everyday life. A 100 mm VAS is used to answer the questions. The mean of the ten questions gives the BASFI score – a value between 0 and 10. If there are missing questions the average of the non-missing items is used (Braun 2009, van Tubergen 2001).

### **5.5.5 ASAS Health Index**

The ASAS health index is a linear composite measure and contains 17 items (dichotomous response option: “I agree” and “I do not agree”).

Each statement on the ASAS Health Index is given a score of 1 = I agree OR 0 = I do not agree. All item scores are summed up to give a total score that ranges from 0 (good functioning) to 17 (poor functioning). Items No 7 and 8 are not applicable for all patients. For those patients who ticked the response “not applicable”, the sum score is analysed based on n=16 or n=15, respectively.

A total score can be analysed if no more than 20% of the data are missing. The total score is calculated as follows for respondents with one to a maximum of three missing responses:

$$\text{sumscore} = \frac{x}{17 - m} \times 17$$

x = Item summation score  
m = Number of missing items

Cases with more than three missing responses cannot be allocated a total score.

### 5.5.6 Bath Ankylosing Spondylitis Metrology Index (BASMI linear)

The BASMI is a validated instrument that uses the minimum number of clinically appropriate measurements that assess accurately axial status, with the goal to define clinically significant changes in spinal movement. Parameters include:

1. lateral lumbar flexion (cm)
2. tragus-to-wall distance (cm)
3. lumbar flexion (modified Schober) (cm)
4. intermalleolar distance (cm)
5. cervical rotation angle (cm)

Additionally, the following assessments should be taken:

6. chest expansion
7. occiput-to-wall distance

The assessments *A* of the first five components into the scores *S* using the equations are given in Table 5-1 (van der Heijde et al, 2013).

**Table 5-1 Equations for the conversion of the assessments A into scores S for the five components of the BASMI linear**

	S = 0 if	Between 0 and 10	S = 10 if
Lateral lumbar flexion* (cm)	$A \geq 21.1$	$S = (21.1 - A)/2.1$	$A \leq 0.1$
Tragus-to-wall distance* (cm)	$A \leq 8$	$S = (A - 8)/3$	$A \geq 38$
Lumbar flexion (modified Schober) (cm)	$A \geq 7.4$	$S = (7.4 - A)/0.7$	$A \leq 0.4$

	S = 0 if	Between 0 and 10	S = 10 if
Intermalleolar distance (cm)	$A \geq 124.5$	$S = (124.5 - A)/10$	$A \leq 24.5$
Cervical rotation angle*(°)	$A \geq 89.3$	$S = (89.3 - A)/8.5$	$A \leq 4.3$

\* For lateral lumbar flexion, tragus-to-wall distance, and cervical rotation the average of right and left should be taken. If a score lies beyond the range 0-10, the values 0 or 10 have to be used, respectively. For facilitating computer calculations with "if... then ... else" fields in a table calculation program such as Microsoft Excel, the limits of the linear ranges are also given. The  $BASMI_{linear}$  is the mean of the five scores.

### 5.5.7 ASAS-NSAID Score

The recommendations by ASAS (Dougados 2010) will be used to score each patient's NSAID use during specific time periods. The components that go into the calculation of the score is the type of NSAID, average daily dose, length in days of the time period of interest and the number of days with NSAID intake within the time period of interest. The final score should be between 0 and 100 but can in rare cases be larger than 100.

The scoring of NSAIDs is described below.

Score	Intake
0	No intake
100	150 mg diclofenac, 600 mg etodolac, 150 mg indometacin, 20 mg piroxicam, 1000 mg naproxen, 90 mg etoricoxib, 200 mg ketoprofen, 20 mg tenoxicam, 200 mg aceclofenac, 200 mg flurbiprofen, 15 mg meloxicam, 400 mg celecoxib, 2400 mg ibuprofen, 400 mg phenylbutazone.

The CRF provided dose information will be handled as follows:

- Doses > maximum dose will be scored as > 100
- Missing doses will be scored with maximum daily dose for the current NSAID (i.e. score of 100)

Drug start and end dates are needed in order to know the number of days an NSAID was prescribed. In case they are missing, the following rules will be used:

- Missing start dates will assume the start date of medication is Day -28 (i.e. prior to start of study drug)
- Missing end dates will assume the end date of medication is the patient's last day in the Study

- If the study drug is ongoing when the patient discontinues then the drug end date will be equal to the day of discontinuation. The period end date will also end on the day of discontinuation

The table below presents the score associated with the dosing frequency as specified by the ASAS definition and how the different database entries will be categorized. The frequency was not consistently specified in the ASAS publication, the below categorization was selected.

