Intra-articular corticosteroids are not permitted within the 4 weeks preceding randomization and up to Week 12. After Week 12, no more than 1 joint per 24-week period may be injected. No single injection should exceed 40 mg of triamcinolone (or equivalent) and the total dose of intra-articular corticosteroid may not exceed 80 mg of triamcinolone (or equivalent) during any 20-week period. Injection of intra-articular steroids is not permitted within 8 weeks prior to Week 20.

Non-steroidal anti-inflammatory drugs (NSAIDs) (including COX-1 or COX-2 inhibitors), low strength opioids and acetaminophen/paracetamol

Patients regularly using NSAIDs, low strength opioids, or paracetamol/acetaminophen should be on stable dose for at least 2 weeks before randomization to allow inclusion. They should remain on a stable dose in the study up to Week 4.

Changes in the NSAID intake will be captured by the patient in the patient diary and checked and be transferred into the eCRF at all scheduled study visits after week 4.

Patients taking low strength opioids or paracetamol/acetaminophen PRN within the 2 weeks before randomization can continue to do so in the study; however, they have to refrain from any intake during at least 24 hours before a visit with disease activity assessment.

After Week 12 assessments are completed, a change in the low strength opioids, or paracetamol/acetaminophen treatment regimen is permitted.

Any change of the low strength opioids, or paracetamol/acetaminophen treatment during the trial should be recorded on the appropriate Prior and Concomitant medication eCRF page.

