#### Secondary objectives:

- H2: Secukinumab 150 mg s.c. (pooled Secukinumab groups) is not different to placebo regimen with respect to change from baseline in ASAS-NSAID score at Week 12
- H3: Secukinumab 150 mg s.c. (pooled Secukinumab groups) is not different to placebo regimen with respect to change from baseline in total BASDAI score at Week 12
- H4: Secukinumab 150 mg s.c. (delayed tapering) is not different to placebo regimen with respect to signs and symptoms (ASAS20 response) at Week 12
- H5: Secukinumab 150 mg s.c. (early tapering) is not different to placebo regimen with respect to signs and symptoms (ASAS20 response) at Week 12
- H6: Secukinumab 150 mg s.c. (early tapering) is not different to placebo regimen with respect to signs and symptoms (ASAS20 response) at Week 16.
- H7: Secukinumab 150 mg s.c. (delayed tapering) is not different to placebo regimen with respect to change from baseline in ASAS-NSAID score at Week 12.
- H8: Secukinumab 150 mg s.c. (early tapering) is not different to placebo regimen with respect to change from baseline in ASAS-NSAID score at Week 12.
- H9: Secukinumab 150 mg s.c. (delayed tapering) is not different to placebo regimen with respect to change from baseline in total BASDAI score at Week 12.
- H10: Secukinumab 150 mg s.c. (early tapering) is not different to placebo regimen with respect to change from baseline in total BASDAI score at Week 12
- H11: Secukinumab 150 mg s.c. (early tapering) is not different to placebo regimen with respect to change from baseline in total BASDAI score at Week 16.

These hypotheses will in principal be tested hierarchically in ascending order. However, since some hypotheses for individual group comparisons are already contained in the higher-ranked, pooled comparisons for the same endpoint (i.e. H4 and H5 are contained in H1, H7 and H8 are contained in H2 and H9 and H10 are contained in H3) these individual hypothesis can be tested simultaneously. The justification is that as soon as the pooled hypothesis has been rejected (e.g. H1), at least one of the two contained individual hypotheses (e.g. H4 and H5) must be false and there is only a potential for at most one type-I-error. Therefore H4 and H5 can be tested simultaneously once all higher-ranked hypotheses have been rejected. The same argument applies to H7 and H8 and to H9 and H10.

The following chart displays the testing strategy graphically:

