### 5.1.3 Concomitant medication date imputation

This algorithm is used when *event* is the partial start date of the concomitant medication.

The following table explains the notation used in the logic matrix. Please note that **missing start dates** will not be imputed.

	Day	Month	Year
Partial CM Start Date	Not used	MON	YYYY
Treatment Start Date (TRTSDT)	Not used	TRTM	TRTY

The following matrix explains the logic behind the imputation.

	MON MISSING	MON < TRTM	MON = TRTM	MON > TRTM
YYYY MISSING	(C2) Uncertain	(C1) Uncertain	(C1) Uncertain	(C1) Uncertain
YYYY < TRTY	(D) Before Treatment Start	(A) Before Treatment Start	(A) Before Treatment Start	(A) Before Treatment Start
YYYY = TRTY	(C2) Uncertain	(A) Before Treatment Start	(C1) Uncertain	(B) After Treatment Start
YYYY > TRTY	(E) After Treatment Start	(B) After Treatment Start	(B) After Treatment Start	(B) After Treatment Start

The following table is the legend to the logic matrix.

Relationship	
Before Treatment Start	Partial date indicates CMD start date prior to Treatment Start Date
After Treatment Start	Partial date indicates CMD start date after Treatment Start Date
Uncertain	Partial date insufficient to determine relationship of CMD start date relative to Treatment Start Date
Imputation Calculation	
(A)	15MONYYYY
(B)	01MONYYYY
(C1 or C2)	IF relative reference start = before treatment start THEN TRTSDT-1 ELSE IF relative reference start = '' THEN TRTSDT+1
(D)	01JULYYYY

(E)	01JANYYYY
-----	-----------

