**Table 5-2 Mapping of dosing frequency to NSAID score**

Frequency	Scores	Database entry
Patient did not take any NSAID during the period of interest	0/7	
<1 day/week	0.5/7	Q2W, MISSING, PRN, UNK, ASNEEDED, QM, Q4W, Q3W
≥1 – <3 days/week	2/7	Q1W, WEEKLY, BIW
≥3 – <5 days/week	4/7	TIW, QIW
≥5 – <7 days/week	6/7	
Everyday	7/7	TID, BID, DAILY, Q24H, QID, QD
Note: Q2W=every 2 weeks, PRN=as needed, UNK=unknown, Q1W=one a week, BIW=twice a week, TIW=three times a week, TID=three times a day, BID=twice a day, QIW= four times a week, Q24H=QID=QD=one a day, QM=one a month; Q4W=one every 4 weeks; Q3W=one every 3 weeks.		

To calculate the NSAID cumulative score the following formula will be used for each NSAID being taken:

$100 * (\text{Daily dose} / \text{pre-specified max dose}) * \text{frequency score} * (\text{min}(\text{medication end date, period end date}) - \text{max}(\text{medication start date, period start date}) + 1 = \text{range of days patient used the medication}) / \text{number of days the patient was in the period.}$

In case a patient takes more than one type of NSAID, changes the dose or the frequency of NSAID during the period of interest, additional scores will be calculated for each new combination and the final score for that patient is the sum of all scores.

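### SAP 5.5.7 dates every NSAID record without a start date to Day -28, so an undated on-study record is counted in the baseline of the ASAS-NSAID change score; the effect is probably small.

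*SAP*

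**What the plan says.** SAP 5.5.7 gives the date rules for the score. For starts: "Missing start dates will assume the start date of medication is Day -28 (i.e. prior to start of study drug". For ends: "Missing end dates will assume the end date of medication is" the patient's last study day. No rule asks whether a record was first entered before or after randomization.

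The scoring text under Table 5-2 of the same section begins "To calculate the NSAID cumulative score the following formula will be used for each NSAID being taken". It multiplies dose share, frequency score and the share of the period's days that the record covers. If the drug, dose or frequency changes, "additional scores will be calculated for each new combination and the final score for that patient is the sum of all scores".

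SAP 2.7.2 puts this endpoint in the confirmatory hierarchy: H2 (pooled), H7 and H8 (single arms) are stated "with respect to change from baseline in ASAS-NSAID score at Week 12". The model is an MMRM on change with baseline ASAS-NSAID as covariate and a baseline-by-visit interaction.

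SAP 5.1.3, on concomitant medication generally, says "Please note that missing start dates will not be imputed". Its matrix nevertheless gives a rule when month and year are both missing: the day before treatment start if the record is flagged as earlier, the day after if the flag is blank. Nothing says which section governs NSAIDs.

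Protocol 5.5.7 describes the data source after Week 4: "Changes in the NSAID intake will be captured by the patient in the patient diary", with transfer to the eCRF at scheduled visits.

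**The concern.** The design expects new NSAID records after randomization. Protocol 3.1 advises step-wise reduction from Week 4 and allows on-demand increases, and each step is a new scored combination. If such a record lacks a start date, the rule places post-randomization intake in the pre-randomization score. SAP 2.1.1 defines the efficacy baseline as the last observation before randomization, so the two do not fit together.

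Three things are at stake. The change score is second in the hierarchy (H2), and every later hypothesis depends on it. An individual patient can be credited with NSAID sparing that did not occur. An inflated baseline can also move a patient across the cut of 75 that defines the subgroups in SAP 2.2.1: a true baseline of 50 plus a back-dated record of 50 becomes 100.

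**Working it through.** **1. The plan's own figures.** The example in Protocol 13.4.1 reproduces: 100 × 120 × (4/7)/180 = 38.1 and 50 × 60 × (2/7)/180 = 4.8, total 42.9. The NSAID power in Protocol 9.7 (63.9 vs 36.6, difference 27.3, SD 40) also reproduces: 62 per arm gives 96.7%, in line with the stated >90%.

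**2. Effect on one patient.** Formula: 100 × (dose/maximum) × frequency × (days of overlap)/(days in period). Assumed windows: baseline Day -28 to -1, and Week 12 period Day 58 to 85 (28 days). Intake is daily, so frequency is 7/7.

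| Undated record | True baseline → Week 12 (change) | Under the rule |
|---|---|---|
| New, full dose, from Day 60, ongoing | 0 → 100 × 26/28 = 92.9 (+92.9) | 100 → 100 (0) |
| New, full dose, Day 33 to 50, end date known | 0 → 0 (0) | 100 → 0 (-100) |
| On 100 at baseline, stopped Day 29; half dose from Day 57 | 100 → 50 (-50) | 150 → 50 (-100) |
| On 100 at baseline, stopped Day 29; full dose from Day 57 | 100 → 100 (0) | 200 → 100 (-100) |
| On 100 at baseline, stopped; full dose from Week 10 | 100 → 100 × 14/28 = 50 (-50) | 200 → 100 (-100) |

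A taper from full to half dose before Day 58 gives the same figures as the third row. Baseline windows of 7 and 14 days give the same result for the new records in the first two rows. With a 70-day window the first row gives 100 × 28/70 = 40 at baseline and a change of +60, so the masking is only partial.

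**3. Effect on the treatment comparison.** The documents give no rate of undated on-study records. Assume 5% of placebo and 1% of secukinumab patients have one, each adding 100 to baseline and covering the whole Week 12 period. The baseline imbalance is 100 × (5% - 1%) = 4 points.

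- *Raw change:* 27.3 - 4 = 23.3.
- *Planned model:* with baseline as covariate, modelling change is equivalent to modelling the Week 12 value adjusted for baseline. The Week 12 value of such a record is right, so the effect moves by 4 × b, where b is the fitted within-arm slope of Week 12 on recorded baseline. Assume a true baseline SD of 20 (variance 400) and a true slope β of 0 to 1. The back-dated records add variance 0.05 × 0.95 × 10,000 = 475 on placebo and 0.01 × 0.99 × 10,000 = 99 in each secukinumab arm, on average (475 + 99 + 99)/3 = 224.3. Then b = β × 400/624.3 = 0.641β, and the shift is 4 × 0.641β = 2.56β, that is 0 to about 2.5 points. Simulation with 63 per arm agrees: 27.5, 26.7, 26.0 and 25.6 for β = 0, 0.25, 0.5 and 0.75.
- *If affected patients also run 50 points higher at Week 12* (a further assumption), b rises by 0.5 × 224.3/624.3 = 0.18 and the shift is 0.7 to 3.3 points.
- *Restarts at Week 10:* the rule also raises the Week 12 score by 50, which makes placebo look worse by 50 × 4% = 2 points. Here b = 0.641β + 0.18 and the net shift is 2 - 4b = 1.28 - 2.56β. The difference widens for β below 0.5, is unchanged at 0.5 and narrows above it (range 28.6 to 26.0).

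**4. Power.** Take 63 per arm (190/3) and SD 40. The standard error is 40 × √(2/63) = 7.13 for a single arm and 40 × √(1/63 + 1/126) = 6.17 pooled. Power is Φ(difference/SE - 1.96).

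| Difference | Single arm (H7, H8) | Pooled (H2) |
|---|---|---|
| 27.3 (planned) | 96.9% | 99.3% |
| 23.3 (raw 4-point shift, no adjustment) | 90.5% | about 96.5% |

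**The case against.** The best defence is that few records are affected. Inclusion criteria 8 and 9 require regular NSAID intake and a stable dose before randomization, so most missing starts should belong to true pre-study drugs, for which Day -28 is sensible. After Week 4 intake is recorded daily and the diary is checked at visits, so undated on-study records should be uncommon. This stands as an argument about frequency. It does not defend the rule, which scores such a record wrongly whenever one occurs.

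Three stronger readings are tempting, and the documents support none of them.

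- *The rule hides placebo restarts and so narrows the NSAID-sparing difference.* That holds for unadjusted change if placebo has more such records. Under the planned adjustment, Week 10 restarts can move the difference either way. Undated taper steps, which overstate the reduction, could be commoner on secukinumab.
- *The trial loses its planned power.* On raw change, with only placebo patients affected, 5% or 10% would cut the difference to 22.3 or 17.3 and single-arm power at 62 per arm to 87% or 67%. Those rates have no source in the documents, and raw change is not the planned analysis.
- *SAP 5.1.3 flatly contradicts 5.5.7.* Section 5.1.3 is a general algorithm for partial dates, and its own matrix assigns dates around treatment start. The sections differ and precedence is unstated, but a specific scoring rule can coexist with a general one.

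**Conclusion.** The point holds as a minor but real error in a derivation rule. As written, SAP 5.5.7 puts an undated on-study NSAID record into the baseline of a confirmatory endpoint. For a single patient at full daily dose the raw change can be wrong by up to 100 points. Exact cancellation for an ongoing record depends on a baseline window within Day -28 to -1, which the SAP does not state.

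For the trial, the shift under the planned model is about 0 to 2.5 points of 27.3 at the assumed 5% and 1% rates, with an assumed baseline SD of 20 and slopes from 0 to 1. It is somewhat more if affected patients also score higher at Week 12. The sign is not settled. At those rates even the unadjusted shift leaves both the single-arm and pooled tests above 90% power. The true rate is unknown and probably low. The reason to act is that the rule is wrong for these records and cheap to correct, not that H2 is in danger.

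**What to change.** Amend SAP 5.5.7 before database lock:

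1. Apply the Day -28 rule only to NSAID records first entered at screening or baseline.
2. For a drug, dose or frequency record first entered later, set a missing start to the day after the last visit at which that combination was not reported, and never before randomization. The rule must refer to the combination, not just the drug, or it will miss a taper step or restart of the same NSAID.
3. State that 5.5.7 takes precedence over 5.1.3 for NSAIDs.
4. State the baseline window for the score, so that the calculation is reproducible.

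The cost is a few sentences and a small programming change. The imputed on-study start may be early, by at most the gap between visits (four weeks between Weeks 8 and 12). The daily diary should usually narrow this, and any remaining error stays in the on-treatment scores and out of baseline. A count of NSAID records with missing starts, by arm and visit of first entry, would show whether the issue arose at all.
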